Purpose: This project studies the impact of two adaptations. One adaptation focuses on increasing the accessibility of the program, which participants report is limited by the requirement of twice-weekly attendance. This project will compare the delivery of CR in either two clinic-based sessions (Clinic) or one clinic and one remote session (Hybrid) per week. The second adaptation is intended to improve personalization of CR by systematically accounting for individual differences in neurocognitive needs. Drawing upon convergent evidence for tailoring CR based on need for early auditory processing (EAP) training, this project integrates a measure of EAP into the baseline assessment to facilitate personalization of the menu of restorative computer-based exercises used in CR. The primary purpose of data analyses is to inform the feasibility and acceptability of the adaptations. The primary outcome will be treatment satisfaction. The secondary outcomes will be change in neurocognition from pre- to post-treatment.

Study Locations: New York State Psychiatric Institute and NYS OMH Facilities:

- ✓ Washington Heights Community Service
- ✓ Creedmoor Psychiatric Center
- ✓ Kingsboro Psychiatric Center
- ✓ Manhattan Psychiatric Center
- ✓ Rockland Psychiatric Center
- ✓ South Beach Psychiatric Center

Description of Subject Population: The study sample includes adults with schizophrenia or schizoaffective disorder who are referred to and eligible for CR2PR.

Procedures: There are two phases of this study.

Phase 1: Staff training and Start up (Months 1-3).

The focus in this initial phase is staff training, using the same combination of web, telephonic and in person training currently in place for CR2PR. Clinic staff trained on cognitive assessment will be provided with and trained to administer the Tone Matching Test as an additional component of the baseline assessment administered for routine CR treatment planning. The CR2PR clinicians will be trained on hybrid delivery methods and to use the Tone Matching Test results to personalize the menu of cognitive exercises such that the treatment plan for only those identified as EAP impaired will include the EAP exercises that are available in the web-based programs used by CR2PR clinics. CR2PR clinicians will be trained on the protocol for Hybrid CR delivery.

Phase 2: Pilot Feasibility Trial (Months 4-36).

The focus of this phase is to implement and evaluate cognitive remediation.

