Throughout treatment in both conditions, CR clinicians document service utilization by tracking scheduled sessions, attendance, treatment dropout and completion. PI [name] will continue to provide supervision of CR clinicians as a part of overseeing the CR2PR program.

Within one week following treatment completion, clients will be assessed for treatment satisfaction and change in neurocognitive functioning by a research assistant. Treatment completion is defined as at least 20 of 30 clinic sessions for the Clinic condition and at least 10 of 15 clinic sessions for the Hybrid condition. A research assistant will conduct a semi-structured debriefing interview with each participant in the Hybrid condition about their experience using remote technology. At Study months 15 and 30, a research assistant will conduct a semi-structured debriefing interview with each CR2PR clinician about remote technology use and how the tone matching test informed the choice of cognitive exercises.

Criteria for Early Discontinuation: Criteria for early discontinuation from the study will follow clinic-based guidelines. A person is discontinued from a service if they are no longer able to attend due to scheduling conflicts (e.g., work/school), hospitalization for medical or substance use treatment, inpatient psychiatric hospitalization, or discharged from the clinic. The CR2PR clinician will use clinical judgment as to the appropriateness of continued participation for each participant, taking into account evidence of clinical worsening, suicidality, or other issues that may arise during participation. Consultation with the PI will be sought through routine supervision prior to discontinuation. No additional criteria will be used for research purposes.

Assessment Measures: Screening measures include the Wechsler Test of Adult Reading (WTAR-5) and Columbia Suicide Severity Rating Scale. The Tone Matching Test is included in the assessment battery to tailor the CR treatment plan. The primary outcome measure will be treatment satisfaction. The secondary outcome will be change in neurocognition from baseline to post-treatment (approximately 15 weeks).

- **The Wechsler Test of Adult Reading (WTAR-5)** will be used to estimate premorbid intellectual functioning and determine eligibility (Full Scale IQ \geq 70). This assessment takes 3-5 minutes.

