- **The Columbia-Suicide Severity Rating Scale** will be used to assess psychiatric stability. Should suicidal ideation or behavior be endorsed, imminent risk will be further evaluated by the assessor and appropriate, immediate action will be taken. This assessment takes 5-10 minutes.
- **The Tone Matching Test (TMT)** consists of pairs of 100-ms tones that are either the same or differ in pitch between 2.5 and 50%, with a 500-ms inter-tone interval. The participant listens to each tone pair and indicates whether the tones were the same or different. A cut-off score of 70% correct classifies EAP as impaired or intact. This test takes approximately 7-10 minutes and will be administered by the designated clinician at each clinic at baseline.
- **Treatment Satisfaction:** Following completion of CR, all clients are asked to complete a questionnaire rating satisfaction with the treatment experience, working alliance with the CR clinician, and perceived benefits from the intervention. Items are rated on a scale of 1 to 6. The outcome measure is an average of all ratings with higher ratings indicating greater satisfaction. This measure takes approximately 2 minutes to complete. Treatment satisfaction will be compared between groups.
- **Neurocognition:** The Brief Assessment of Cognition in Schizophrenia (BACS) is a standardized battery. Selected subtests will assess verbal memory, working memory, speed of processing, and executive function. The tests will take approximately 25 minutes to complete. It is routinely administered by a designated CR2PR clinician at each clinic before treatment. A trained research assistant will administer the battery at post-treatment. The Continuous Performance Test – Identical Pairs (CPT-IP) is a computerized test that assesses attention/vigilance. Participants view numbers flashed on a computer screen and are to respond when the same number appears twice in a row. The test takes 14 minutes to complete. It is routinely administered by the designated CR2PR clinician at each clinic before treatment. A trained research assistant will administer the test at post-treatment. The outcome measure is an average T score from all neurocognitive subtest T scores. Change in neurocognition will be compared between groups.

Research Related Delay to Treatment: Research procedures will not result in a delay to treatment. All clients will have access to the Cognitive Remediation program provided routinely at their clinic.

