## **Improving Accessibility and Personalization of Cognitive Remediation for Schizophrenia**

Statistical analyses for this project will focus on the comparison of proximal outcomes between Clinic and Hybrid delivery methods of Cognitive Remediation. There are two proximal outcomes: Treatment Satisfaction (primary) and Neurocognition (secondary).

Wilcoxon's rank sum test will be used to compare Clinic and Hybrid CR groups on treatment satisfaction at post-treatment and change on the average neurocognitive T score from baseline to post-treatment.

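### As written, both outcomes are assessed only after treatment completion, so the Wilcoxon tests may compare completers selected after randomization on the attendance burden that Hybrid is meant to reduce

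*Protocol*

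**What the plan says.** Participants are randomized to Clinic or Hybrid after the baseline assessment (Protocol, Procedures). The same section sets the timing of both outcomes: "Within one week following treatment completion, clients will be assessed for treatment satisfaction and change in neurocognitive functioning by a research assistant". The next sentence defines treatment completion as "at least 20 of 30 clinic sessions for the Clinic condition and at least 10 of 15 clinic sessions for the Hybrid condition". Remote work does not count towards completion in Hybrid.

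Assessment Measures repeats the trigger for the primary outcome: "Following completion of CR, all clients are asked to complete a questionnaire rating satisfaction with the treatment experience". It places the post-treatment neurocognitive measurement at roughly 15 weeks.

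Clinicians record service use in both arms by "tracking scheduled sessions, attendance, treatment dropout and completion", so non-completers will be known. No post-treatment assessment of them is described.

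The SAP states: "Wilcoxon's rank sum test will be used to compare Clinic and Hybrid CR groups on treatment satisfaction at post-treatment". The same test is used for change in the average neurocognitive T score. The SAP text available to me names no analysis set and no rule for missing outcomes. I did not have the whole SAP file, so that remark covers only the part I read.

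**The concern.** Randomization protects a comparison of everyone randomized. It does not protect a comparison of those who later meet an attendance threshold, unless meeting it is unrelated to arm or to outcome. Here a link with arm is plausible on the trial's own reasoning. The Purpose section says that access to the current program is "limited by the requirement of twice-weekly attendance", and Hybrid halves the clinic visits. Criteria for Early Discontinuation adds: "A person is discontinued from a service if they are no longer able to attend due to scheduling conflicts". Hybrid may therefore keep people whom Clinic loses.

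A link with outcome is also plausible. People who found attendance hard may rate the treatment differently and may change differently on cognitive tests. Their ratings bear directly on acceptability, which the Purpose section makes a main aim of the analysis. If they are never asked, no later analysis can recover their answers.

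**Working it through.** The documents state no sample size, power, significance level or expected dropout, so there is no planned figure to reproduce. I checked three things.

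**1. Is the rule the same in both arms?** Inputs are from Protocol, Procedures.

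- As a share of scheduled clinic sessions: 20/30 = 10/15 = 66.7%. The rule is the same.
- As visits per week over 15 weeks: 20/15 = 1.33 in Clinic and 10/15 = 0.67 in Hybrid. The burden is not the same. A person who can come only once a week has 15 visits by week 15, which is a completer in Hybrid and a non-completer in Clinic. That is the access gain Hybrid seeks, and it is also a route to selection.

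**2. Does the rule by itself separate the arms?** Assume that every scheduled visit is kept independently with the same chance p. Completion is P(X ≥ 20) with X ~ Bin(30, p) in Clinic and P(X ≥ 10) with X ~ Bin(15, p) in Hybrid.

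| p | Clinic | Hybrid |
|---|---|---|
| 0.5 | 4.9% | 15.1% |
| 0.6 | 29.1% | 40.3% |
| 0.7 | 73.0% | 72.2% |
| 0.8 | 97.4% | 93.9% |

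The gap changes sign near 70% attendance. If people instead attend every session until they drop out, both thresholds are reached at week 10 (20 visits at two a week, 10 at one a week), and the rule selects equally. Any separation must therefore come mainly from attendance itself differing by arm.

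**3. How large could the distortion be?** This is an illustration; none of these inputs is in the documents. Assume no true difference, normally distributed engagement, assessment of the most engaged share q in each arm, and correlation r between engagement and outcome. Mean engagement among those assessed is m(q) = φ(z)/q, with z the normal quantile at 1 − q. The false difference is r × [m(Clinic) − m(Hybrid)].

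The values are m(0.8) = 0.350, m(0.7) = 0.497, m(0.6) = 0.644 and m(0.5) = 0.798.

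| Assessed, Clinic v Hybrid | r = 0.1 | r = 0.3 | r = 0.5 |
|---|---|---|---|
| 70% v 80% | 0.015 SD | 0.044 SD | 0.073 SD |
| 60% v 80% | 0.029 SD | 0.088 SD | 0.147 SD |
| 50% v 80% | 0.045 SD | 0.134 SD | 0.224 SD |

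With these shares, the false difference favours Clinic if r is positive and Hybrid if r is negative.

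A simulation of the Wilcoxon test under the same model used 3,000 runs per setting, 30 to 100 per arm, r of 0.3 to 0.5 and two-sided 5%, all assumed:

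- Completers only, 60% v 80%: false-positive rate about 6 to 14%.
- Completers only, 50% v 80%: about 6 to 26%.
- Completers only, 70% in both arms with the same selection: about 5%, no bias.
- Everyone randomized: about 4 to 6%, which is nominal within simulation error.

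**The case against.** The strongest reply is that the rule is fair. It asks for the same two-thirds of scheduled clinic sessions in each arm. A reader might infer from 20 against 10 visits that the arms are selected by different rules. The first two checks do not support that. Equal visit counts would not cure the problem either, because the difficulty is selecting on attendance at all.

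A reader might also infer that a once-weekly attender is assessed at week 10 in Hybrid and week 20 in Clinic. The documents do not support this. The threshold is a minimum for counting as a completer, not a stopping point; Hybrid runs for 15 weeks; post-treatment is put at about 15 weeks; and no extension of Clinic is described.

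Third, the plan never says that non-completers are excluded. That is correct: it is silent, and the satisfaction item does refer to all clients, though after completion of CR. The point stands only for the plan followed as written. If the sponsor already intends to assess everyone, a sentence saying so settles it.

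Fourth, this is a pilot feasibility trial, and asking about satisfaction after a substantial course is a defensible question. Both are fair. Even so, the SAP specifies between-arm tests on both outcomes, and a difference among completers would be read as a difference between delivery methods.

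**Conclusion.** The concern holds in a limited form. Followed as written, the plan assesses completers only, and completion is a post-randomization event based on the burden that Hybrid is designed to reduce. The Wilcoxon comparisons may therefore be between differently selected groups, for the primary and the secondary outcome alike.

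The size and direction of any bias cannot be derived from the documents. The illustrated 0.01 to 0.22 SD rests on assumed completion gaps of 10 to 30 percentage points and assumed correlations of 0.1 to 0.5. A reader might infer that the comparison is biased towards Hybrid, or biased for certain; neither follows. If the arms complete at the same rate and by the same kind of selection, there is no bias. The change is worth making because it is cheap and the missing outcomes cannot be collected afterwards.

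**What to change.** Replace the completion trigger in Procedures, and the matching wording under Treatment Satisfaction, with an offer of the post-treatment assessment at about week 15 after starting treatment to everyone randomized, whatever their attendance. In the SAP, run both Wilcoxon tests on all assessed participants by randomized arm, and give completers as a supportive analysis. The completion definition stays for that purpose.

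If someone leaves early and is unlikely to return, take the 2-minute satisfaction questionnaire at discontinuation as a fallback. Keep neurocognition at about week 15 where the person is able and willing, because testing at discontinuation would make its timing depend on dropout. Report by arm how many were not assessed and how many attended no session; the latter can take the cognitive tests but cannot rate the treatment.

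Staff and measures stay the same. Each added full assessment costs the $60 payment (Compensation or Reimbursement) and about 25 + 14 + 2 = 41 minutes (Assessment Measures). Assuming 50 to 100 randomized and 20 to 40% non-completers, neither figure being in the documents:

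- Low: 50 × 0.2 = 10 assessments, $600, 10 × 41/60 = 6.8 hours.
- High: 100 × 0.4 = 40 assessments, $2,400, 40 × 41/60 = 27.3 hours.

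Some people will decline, some early leavers will rate a partial course, and some who are hospitalized or clinically worse cannot be tested. The change therefore reduces the selection but does not remove it, which is why the numbers not assessed need reporting by arm.

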## **Improving Accessibility and Personalization of Cognitive Remediation for Schizophrenia**

Statistical analyses for this project will focus on the comparison of proximal outcomes between Clinic and Hybrid delivery methods of Cognitive Remediation. There are two proximal outcomes: Treatment Satisfaction (primary) and Neurocognition (secondary).

Wilcoxon's rank sum test will be used to compare Clinic and Hybrid CR groups on treatment satisfaction at post-treatment and change on the average neurocognitive T score from baseline to post-treatment.

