3. Traumatic brain injury in the last 2 years

Client report; Medical chart review

Procedures: A trained research assistant will obtain informed consent, screen for eligibility and obtain additional sociodemographic information. Participants will complete the standard CR2PR neurocognitive assessment battery plus the TMT with a trained clinician. Following completion of the baseline assessment, participants will be randomized using a pre-determined randomization sequence made by the research team to either Clinic or Hybrid CR.

Clinic CR: This is the evidence-based CR intervention currently in use at the OMH clinics. The Clinic research arm consists of 30 sessions delivered at 2 times per week in a group format of up to 8 participants with rolling admission. Each session consists of 45 minutes of working on 3-4 computerized exercises to improve specific cognitive skills. CR2PR clinicians are trained to select cognitive exercises from a menu of web-based programs to improve the cognitive functions identified as impaired on the assessment, e.g., attention, memory. With the addition of the TMT, they will be able to identify EAP as a focus area. Computer exercises are followed by 15-minute manualized discussion groups which promote generalization of cognitive gains on computer activities to functional gain by encouraging participants to link within-session cognitive activities to daily activities and recovery goals.

Hybrid CR: The Hybrid condition consists of 15 clinic sessions in the above format, and independent work on cognitive exercises for 60 minutes per week for 15 weeks using a laptop, PC or tablet available to them (at home, school, clinic, library). Independent work on designated web-based computer exercises can be done in multiple or in one sitting. Clients will keep logs of their activities and issues related to remote practice. During the in-clinic session, the clinician will review their remote activities, problem-solve any access or activity related issues, provide personalized bridging, encouragement and feedback, and review the exercises to be completed remotely before the next clinic-based session. Clinicians will also maintain logs of their experiences with remote sessions to document issues pertinent to feasibility and effectiveness.

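### Neurocognitive change is tested without baseline adjustment, and the SAP's analysis statement names no estimate or interval for either outcome: a cheap improvement, not an error

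*SAP*

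**What the plan says.** The SAP's analysis statement, under the study title, has one operative sentence: Wilcoxon's "rank sum test will be used to compare Clinic and Hybrid CR groups" on two variables. These are post-treatment satisfaction (primary) and "change on the average neurocognitive T score from baseline to post-treatment" (secondary). It names no covariate, effect estimate or interval for either.

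The protocol's Assessment Measures section defines the secondary variable: "The outcome measure is an average T score from all neurocognitive subtest T scores". It adds only that change is compared between groups.

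Three other protocol statements matter here:
- Procedures fixes the order of baseline and allocation: "Following completion of the baseline assessment, participants will be randomized using a pre-determined randomization sequence". The baseline score is therefore a pre-randomization covariate.
- Procedures also ties follow-up to completion: "Within one week following treatment completion, clients will be assessed for treatment satisfaction and change in neurocognitive functioning by a research assistant". For one arm, "Treatment completion is defined as at least 20 of 30 clinic sessions for the Clinic condition"; for Hybrid the threshold is 10 of 15.
- Purpose states the aim: "The primary purpose of data analyses is to inform the feasibility and acceptability of the adaptations".

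Part of the SAP was not available for this review. What is said here about missing items covers only the analysis statement and the protocol.

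**The concern.** There are two separate gaps.

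The first is reporting. A rank-sum p-value does not say how large a Clinic-Hybrid difference remains compatible with the data. In a pilot whose analyses are meant to inform feasibility and acceptability, a difference with an interval is more useful. This holds whatever the correlation between baseline and follow-up.

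The second is efficiency. A change score subtracts the whole baseline value, as if the slope of follow-up on baseline were 1. If the true slope is lower, the change score carries noise that a fitted slope would remove. It also carries chance imbalance: with equal SDs and correlation r, a baseline difference of 2 T points between arms shifts the expected difference in change by 2(1 - r). That is 1.0, 0.6 and 0.2 points at r = 0.5, 0.7 and 0.9.

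**Working it through.** **Inputs.** From the documents: the test, the variable, and baseline measured before randomization. The available text gives no sample size, allocation ratio, significance level, effect size, SD, correlation or dropout rate, so there is no planned figure to reproduce. Assumed: 30 analysed per arm, 1:1, two-sided 5%, true difference 0.4 baseline SD (4 T points if the SD is 10), correlation r from 0.5 to 0.9, complete outcomes.

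**Variance.** Set the baseline SD to 1 and the post-treatment SD to k. The true slope is kr.
- Var(change) = k² + 1 - 2kr
- Var(baseline-adjusted) = k²(1 - r²)
- Excess of change over adjusted = (1 - kr)²

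The excess vanishes when the slope is 1. With k = 1 the ratio of adjusted to change variance is (1 - r²) / [2(1 - r)] = (1 + r)/2, which is 0.75, 0.80, 0.85, 0.90 and 0.95 at r = 0.5, 0.6, 0.7, 0.8 and 0.9.

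**Power.** Simulated with 20,000 runs per cell, equal SDs, 30 per arm. Each cell gives power in % for the planned rank-sum test on change, then for the rank-sum test on residuals from post on baseline, fitted without arm.

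| Residuals | r = 0.5 | 0.6 | 0.7 | 0.8 | 0.9 |
|---|---|---|---|---|---|
| Normal | 32, 40 | 38, 45 | 48, 54 | 65, 69 | 92, 93 |
| t(3) | 43, 65 | 53, 71 | 67, 80 | 86, 91 | 99, 99 |
| Exponential | 41, 68 | 52, 74 | 67, 82 | 85, 91 | 98.5, 98.8 |

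For normal residuals the gains are 8, 7, 6, 4 and 1 points. A repeat with 10,000 runs gave 32/48/91 against 39/53/92 at r = 0.5/0.7/0.9, hence about 5 to 8 points at r = 0.5 to 0.7. With normal residuals and 20 per arm the figures at r = 0.5 and 0.7 are 22, 27 and 34, 38; with 50 per arm they are 49, 61 and 70.5, 77. Type I error was 4.6 to 5.3% for both rank tests.

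**Unequal SDs.** With k = 0.8 the residual test gained 3.5 to 41 points across the residual shapes. With k = 1.2 the change was -1.5 to +16 points. The loss was at r = 0.8, where the slope is 1.2 × 0.8 = 0.96. With k = 1.35, r = 0.7 and exponential residuals the slope is 1.35 × 0.7 = 0.945, and power fell from 62.3 to 59.8%, a loss of 2.5 points.

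**Intervals.** Mean 95% CI half-width in baseline SD at r = 0.5/0.7/0.9, 30 per arm; coverage was 94 to 96%.

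| Residuals | Hodges-Lehmann on change | Adjusted mean difference | Inverted residual rank test |
|---|---|---|---|
| Normal | 0.528/0.410/0.236 | 0.449/0.370/0.226 | 0.457/0.375/0.228 |
| t(3) | 0.441/0.326/0.178 | 0.427/0.349/0.216 | 0.337/0.274/0.166 |
| Exponential | 0.454/0.330/0.175 | 0.445/0.367/0.224 | 0.319/0.264/0.159 |

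The inverted interval is almost as narrow as the adjusted-mean interval with normal residuals, and the narrowest of the three otherwise.

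**Dropout.** One constructed case: no true effect, 40 randomized per arm, about 26% lost, retention dependent on the outcome residual in one arm only (logit slope 0.8). At r = 0.5/0.7/0.9, type I error was 8.6/10.2/11.0% for the planned test and 10.9/11.2/11.4% for the residual test. With 25% lost completely at random it was 4.4 to 5.6% for both.

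**The case against.** The strongest case is that nothing is broken. Protocol and SAP agree that change is compared between groups, the test holds its level, the outcome is secondary, and no available text claims power for it. All of this stands.

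The size of the gain rests on assumed inputs. The outcome averages several subtests, which tends to reduce skew and so favours the cells with smaller gains. That also stands, and it makes the missing estimate and interval the firmer part of the point.

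A Hodges-Lehmann shift on change would close the reporting gap by itself and match the planned test. That is a reasonable minimum. It forgoes the efficiency gain, and its interval was wider than the inverted residual interval in every cell tabulated.

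A reader might infer that linear ANCOVA should replace the rank test. The calculations do not support this: ANCOVA's power minus that of the planned test, at r = 0.5/0.6/0.7/0.8/0.9, is +10/+9/+8/+6/+2 points with normal residuals but +3/-2/-8/-13/-6 with exponential ones. The documents say nothing about residual shape.

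A reader might also expect adjustment to deal with selection, since follow-up is tied to completion. It does not, and in the dropout case above the residual test did slightly worse. That is only one mechanism; selection on baseline could favour adjustment.

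**Conclusion.** The point holds as a low-cost improvement to consider. Under the assumed inputs with normal residuals and equal SDs, the gain is about 5 to 8 points of power at correlations of 0.5 to 0.7, 4 at 0.8 and at most 1 at 0.9. It is larger with skewed or heavy-tailed residuals, or if the post-treatment SD is below the baseline SD. Where the true slope is near 1 there is little or no gain, and losses of about 1 to 3 points appeared in the cells simulated; that is not a bound.

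Two stronger readings are not supported. The planned test is not invalid: its level holds under randomization with complete outcomes or ignorable dropout. Nor can it be said that the SAP as a whole lacks an estimate or interval, because part of it could not be seen. The primary test is unaffected.

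**What to change.** **Secondary outcome.** Prespecify Wilcoxon's rank-sum test on residuals from a regression of post-treatment on baseline average T score, fitted without arm. Report the shift and 95% CI obtained by inverting that test: subtract a trial shift from one arm's post-treatment scores, refit, retest, and keep the shifts not rejected. Test and interval then agree. The baseline-adjusted mean difference with its 95% CI may be added as a supplement. Keep the planned test on change as a sensitivity analysis.

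**Satisfaction.** There is no baseline value, so keep the planned test and report a Hodges-Lehmann shift with 95% CI.

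**Both.** State that these analyses assume complete outcomes or ignorable dropout.

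**Cost.** A few sentences in the SAP, with no new data or participants. In return the analysis takes on one fitted slope and a linearity assumption, the possible small loss near slope 1, and no protection against non-ignorable dropout, which needs separate handling.
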